### 10.3 SIX-MINUTE WALK TEST

The 6MWT is performed at Screening (optional), Baseline, Week 0 (Cohort 1 only), Week 3, Week 6, Week 12, and Week 24 or premature termination. At each of these visits, 6MWT recovery monitoring (heart rate and oxygen saturation measurements) will occur immediately prior to walk, immediately upon stopping the walk, 1 minute post walk, 2 minutes post walk, and 3 minutes post walk. The listing of 6MWT will include the assessment date/time; any Remodulin, oral treprostinil, Tyvaso, and Ventavis dosing information prior to the 6MWT assessment, as applicable; as well as whether subject attempted walk test (yes/no), reason not attempted (if applicable), total distance walked, Borg dyspnea score, oxygen receipt, and unusual circumstances. Recovery monitoring data (time point, heart rate, oxygen saturation, and total recovery time [minutes]) will be listed separately.

The summary of 6MWT will include the number (percentage) of subjects who received oxygen during the test and experienced any unusual circumstances during the test for each cohort.

The summary of 6MWD will include descriptive statistics for total distance walked by assessment visit and time point for each cohort. Changes from Baseline to each post-Baseline time point in total distance walked will also be summarized by cohort and compared within cohort using a Wilcoxon signed-rank test. P-values will be calculated for descriptive purposes; no formal hypothesis testing is planned.

As a sensitivity analysis, total walk distance data will be imputed using the LOCF method, regardless of the reason for early termination. The summary based on this imputation will follow the same layout as the no imputation analysis described above, while again using the Wilcoxon signed-rank test for descriptive purposes; no formal hypothesis testing is planned.

The summary of 6MWT recovery monitoring will include descriptive statistics for each cohort of heart rate (bpm) and oxygen saturation (%) at each of the 5 time points of assessment at each visit, as well as descriptive statistics of total recovery time (minutes).

#### 10.4 BORG DYSPNEA SCORE

The Borg dyspnea score is a 10-point scale rating the maximum level of dyspnea experienced during the 6MWT. Scores range from 0 (for the best condition) to 10 (for the worst condition). The Borg dyspnea score is captured in tandem with the 6MWT at Screening (optional), Baseline, Week 0 (Cohort 1 only), Week 3, Week 6, Week 12, and Week 24 or premature termination, and will therefore be included in the 6MWT listing. The summary of Borg dyspnea score will present descriptive statistics of the Borg dyspnea score at each assessment time point by cohort. Change from Baseline will also be summarized by cohort.

### 10.5 PAH SYMPTOMS

PAH symptoms (fatigue, dyspnea, edema, dizziness, syncope, chest pain, and orthopnea) will be assessed at the Baseline visit prior to the initiation of oral treprostinil and at all subsequent visits, including each day during the Cohort 1 inpatient hospital stay. Scores range from 0 (no symptom experienced) to 3 (symptom severe or frequent). The scores for each symptom will

be listed for each cohort, subject, and time point in chronological order. The scores for each symptom will be categorically summarized separately by cohort at each visit assessment. Shifts from Baseline will also be summarized utilizing category shifts as well as descriptive statistics at each post-Baseline visit separately by cohort.

### 10.6 PANAMA FUNCTIONAL CLASS

The Panama Functional Class is collected at Screening, Baseline, Week 3, Week 6, Week 12, and Week 24 or premature termination. The listing will include the date of assessment and the functional class (I, II, IIIa, IIIb, and IV). The summary table will use descriptive statistics to present the number (percentage) of subjects within each functional class at each time point starting from Baseline. Shifts from Baseline will also be summarized utilizing the categories improved, no change, and deteriorated at each post-Baseline visit separately by cohort.

#### 10.7 WHO FUNCTIONAL CLASS

The WHO Functional Class is collected at Screening, Baseline, Week 3, Week 6, Week 12, and Week 24 or premature termination. The listing will include the date of assessment and the functional class (I, II, III, and IV). The summary table will use descriptive statistics to present the number (percentage) of subjects within each functional class at each time point starting from Baseline and shifts from Baseline by cohort.

#### 10.8 N-TERMINAL PRO-BRAIN NATRIURETIC PEPTIDE

The NT-proBNP is collected at Baseline prior to starting oral treprostinil and repeated at Week 12 and Week 24 or premature termination. All results will be listed by cohort, subject, and assessment time point. The results will then be summarized using descriptive statistics at each time point and paired changes from Baseline by cohort.

## 10.9 PEDIATRIC QUALITY OF LIFE INVENTORY

Health-related QOL will be assessed via the 23-item child and parent PedsQL questionnaire at Baseline, Week 12, and Week 24 or premature termination. The listings of both child and parent inventories will include the date of assessment, which report was used (young child, child, or teen), and the answers to the physical, emotional, social, and school functioning scale questions.

The PedsQL questionnaire is converted to 6 scores for summarization and interpretation: 4 scale scores (1 each for Physical Functioning, Emotional Functioning, Social Functioning, and School Functioning), a Psychosocial Health Summary Score, and a Total Scale Score. For ease of interpretability, items are reverse scored and linearly transformed to a 0 to 100 scale, so that higher scores indicate better quality of life. To reverse score, the 0 to 4 scale items are transformed to 0 to 100 as follows: 0=100, 1=75, 2=50, 3=25, 4=0.

To create scale scores, the mean is computed as the sum of the items over the number of items answered (this accounts for missing data). If more than 50% of the items in the scale are missing, the scale score will not be computed. To create the Psychosocial Health Summary Score, the mean is computed as the sum of the items over the number of items answered in the Emotional, Social, and School Functioning Scales combined. To create the Total Scale Score, the mean is computed as the sum of all the items over the number of items answered on all the scales.

The summaries of both child and parent inventories will present descriptive statistics for each of the 6 scores by cohort, as well as changes from Baseline to both post-Baseline visits.

## 10.10 CARDIAC MAGNETIC RESONANCE IMAGING

Cardiac magnetic resonance imaging assessments were performed on all subjects aged 10 years and older at Baseline and Week 24 or premature termination. The following parameters were evaluated:

- Right ventricular (RV) mass index
- RV ejection fraction (RVEF)
- Left ventricular (LV) ejection fraction (LVEF)
- RV end-diastolic volume (RVEDV) index
- RV end-systolic volume (RVESV) index
- RV stroke volume index
- LV stroke volume index
- RV cardiac output indext

The cMRI measurements from images will be analyzed by a centralized specialist to control for bias and to reduce inter-reader variability. The results of these analyses will be transferred

Final: 15 Aug 2017 Confidential Page 17

to UTC for inclusion in the final study results. The listing of cMRI assessments will include the date/time of assessment as well as the parameters noted above for each visit assessment.

The summary of cMRI parameters will include descriptive statistics for each parameter at each visit as well as changes from Baseline by cohort. The following additional exploratory parameters, if collected, may also be included:

- Flow pattern through the main pulmonary artery by phase-sensitive gradient echo imaging
- Flow pattern through the right pulmonary artery by phase-sensitive gradient echo imaging
- Flow pattern through the ascending aorta by phase-sensitive gradient echo imaging
- RV:LV end-systolic diameter ratio
- Systolic septal flattening
- Right atrial size
- Presence of congenital heart disease
- Atrial or ventricular shunt

### 11 SAFETY ANALYSES

All safety summaries will be performed on the Safety population (see Section 7).

## 11.1 EXTENT OF EXPOSURE

Oral treprostinil dosing will be listed by cohort and subject. The listing will include the date/time of initial oral treprostinil dose, the initial dose (mg), and all subsequent dose changes with start date, morning dose, midday dose, and evening dose.

Remodulin dosing will be listed by subject for Cohort 1 subjects only. The listing will include the initial Remodulin dose (ng/kg/min) and all changes during the study, including the start date/time of the new dose as well as the new dose (ng/kg/min).

Tyvaso dosing will be listed by subject for Cohort 2 subjects only. The listing will include the number of initial Tyvaso breaths per session, the number of initial Tyvaso sessions per day, and all changes during the study; including the start date of new dose, number of breaths per session, and number of sessions per day.

Ventavis dosing will be listed by subject for Cohort 2 subjects only. The listing will include the initial Ventavis dose (X mcg with X mcg/mL), the number of initial Ventavis sessions per

day, and all changes during the study, including the start date of new dose, new dose, and number of sessions per day.

The oral treprostinil dosing and exposure summary will include descriptive statistics for initial oral treprostinil dose, oral treprostinil dose when Remodulin dose is 0.0, oral treprostinil dose at time of hospital discharge, oral treprostinil dose when subject is first off Tyvaso/Ventavis, and final oral treprostinil dose (mg) by cohort. Oral treprostinil dose will be calculated as the sum of the doses administered on a given day divided by the number of doses administered that day. The Remodulin dosing and exposure summary will include descriptive statistics for initial Remodulin dose (ng/kg/min). The Tyvaso dosing and exposure summary will include descriptive statistics for initial Tyvaso breaths per session and a categorical summary of number of initial Tyvaso sessions per day. The Ventavis dosing and exposure summary will include descriptive statistics for initial Ventavis dose per session and a categorical summary of number of initial Ventavis sessions per day.

Oral treprostinil doses will be plotted over time for each individual subject using a different plot for each cohort. The mean oral treprostinil doses will then be plotted over time on a single plot by cohort. Remodulin doses will be plotted over time for each individual subject (Cohort 1 only). Tyvaso doses will be plotted over time for each individual subject (Cohort 2 only).

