4.1 INCLUSION CRITERIA

A subject is eligible for inclusion in this study if all of the following criteria apply:

- 1. Legal guardian informed consent and subject assent, if appropriate, to participate in the study is voluntarily given.
- 2. The subject is between 7 and 17 years of age, inclusive, on the date informed consent is signed.
- 3. *Cohort 3:* The subject must weigh a minimum of 22 kg at Screening.
- 4. The subject has a current diagnosis of PAH (WHO Group I) associated with:
 - a. Idiopathic or heritable PAH
 - b. Persistent PAH for at least one year following surgical repair of a congenital systemic-to-pulmonary cardiac shunt, congenital heart disease, or other congenital heart lesions with no clinically significant residual defects and condition is stabilized hemodynamically
 - c. PAH in subjects with unrepaired restricted atrial septal defect, ventricular septal defect, or patent ductus arteriosus; subject must have a resting postductal oxygen saturation (off oxygen) of greater than 88%
- The subject has a current diagnosis of PAH confirmed by right heart catheterization (RHC) prior to the Screening visit with the following parameters:
 - a. Mean pulmonary arterial pressure (mPAP) of ≥25 mmHg
 - b. Pulmonary vascular resistance index (PVRi) of >3 Wood Units * m²
 - c. Left ventricular end diastolic pressure (LVEDP) or pulmonary capillary wedge pressure (PCWP) of ≤15 mmHg

- 6. Cohort 1: The subject must have been receiving IV/SC Remodulin for at least 90 days without dose change for at least 30 days prior to Baseline. The IV/SC Remodulin dose will be between 25-75 ng/kg/min, inclusive, for the first five subjects in the cohort. Following a safety review, the dose range may be expanded to 25-125 ng/kg/min, inclusive, for the remaining subjects. Subjects must be receiving stable doses of all other PAH medications for at least 14 days prior to the Baseline assessments; exception for diuretics and anticoagulants as outlined in Section 4.3.1.
- 7. Cohort 2: The subject must have been receiving inhaled prostacyclin for at least 90 days and has been at the current stable dose without changes for at least 30 days prior to Baseline. Subjects must be receiving stable doses of all other PAH medications for at least 14 days prior to the Baseline assessments; exception for diuretics and anticoagulants as outlined in Section 4.3.1.

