6.1.1 Cohort 1: IV/SC Remodulin to Oral Treprostinil Transition

Once all entry criteria have been met and Baseline assessments completed, subjects should begin transition in the hospital from IV/SC Remodulin to oral treprostinil with a goal for complete transition off of IV/SC Remodulin within five days of the start of the transition. If possible, Day 5 (or final day of hospital stay if transition occurred in less than 4 days) of hospital stay should be reserved as an observational period for subjects successfully transitioned to oral treprostinil and no longer receiving IV/SC Remodulin. A cross titration will occur so that the dose of IV/SC Remodulin is decreased as the dose of oral treprostinil is increased. Once subjects have been transitioned off IV/SC Remodulin, the dose of oral treprostinil may continue to be titrated to the appropriate optimal dose for that subject throughout the rest of the study.

Dosing guidelines:

• The following equation can be used to estimate a comparable total daily dose of oral treprostinil (in mg) using the subject's dose of IV/SC Remodulin (in ng/kg/min) and weight (in kg):

Oral treprostinil total daily dose (mg) = 0.0072 x Remodulin dose (ng/kg/min) x weight

- IV/SC Remodulin should not be decreased more than 30 ng/kg/min within a 24 hour period
- Oral treprostinil should be increased in proportion to Remodulin decreases and the subject's weight
- IV/SC Remodulin doses should be adjusted (i.e., decreased) at the same time oral treprostinil dose is increased

Hospital Day	IV/SC Remodulin (ng/kg/min)	Oral Treprostinil (mg)		
Day 1 (0-24 hours)	Day 1 (0-24 hours)			
Morning (upon admission)	65	0		
Midday	59	0.5		
Evening	53	1		
Day 2 (24-48 hours)				
Morning	47	1.5		
Midday	41	2		
Evening	35	2.5		
Day 3 (48-72 hours)				
Morning	29	3		
Midday	23	3.5		
Evening	17	4.		
Day 4 (72-96 hours)				
Morning	11	4.5		
Midday	5	5		
Evening	0	5.5 (target dose)		
Day 5 (96-120 hours): Observational period prior to hospital discharge				
Morning	0	continue to titrate if appropriate		
Midday	0	continue to titrate if appropriate		
Evening	0	continue to titrate if appropriate		

Example TID Dosing Schedule for a 35 kg Subject:

Hospital Day	IV/SC Remodulin (ng/kg/min)	Oral Treprostinil (mg)	
Day 1 (0-24 hours)			
Morning (upon admission)	65	0	
Midday	61	0.25	
Early Evening (PM #1)	57	0.5	
Late Evening (PM #2)	53	0.75	
Day 2 (24-48 hours)			
Morning	48	1.125	
Midday	44	1.375	
Early Evening (PM#1)	40	1.625	
Late Evening (PM #2)	36	1.875	

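### SAP 11.1 reports oral treprostinil only as mg per administration, so Cohort 1 dose means mix body weight with dose intensity and the by-cohort plot has no size-adjusted scale

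*SAP*

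**What the plan says.** SAP 11.1 (Extent of Exposure) plans descriptive statistics for the initial oral dose, the dose once Remodulin reaches zero, the dose at hospital discharge, the "oral treprostinil dose when subject is first off Tyvaso/Ventavis, and final oral treprostinil dose (mg) by cohort". The dose being summarised is "calculated as the sum of the doses administered on a given day divided by the number of doses administered that day", that is, mg per administration. For the figures, "The mean oral treprostinil doses will then be plotted over time on a single plot by cohort" (Figure 14.2.5.4). Neither the SAP text nor its lists of tables, listings and figures contains an oral dose in mg/kg or in ng/kg/min equivalents. In the same section, Remodulin is summarised in ng/kg/min.

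Protocol 6.1.1 offers an estimating equation for Cohort 1: "Oral treprostinil total daily dose (mg) = 0.0072 x Remodulin dose (ng/kg/min) x weight". It adds that "Oral treprostinil should be increased in proportion to Remodulin decreases and the subject's weight". Protocol 6.1.4, which is not restricted to one cohort, converts an oral daily dose back to ng/kg/min by multiplying by 139 and dividing by weight.

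Cohorts 2 and 3 (Protocol 6.1.2 and 6.1.3) start at a fixed 0.125 mg and escalate in fixed mg steps, with no weight term. TID and QID regimens are both allowed in every cohort (Protocol 6.1).

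**The concern.** The dose that children reach is part of what this study will tell prescribers about tolerability. Where dose is set in proportion to weight, a mean in mg depends partly on the size of the children enrolled, and its SD includes the spread in size. A reader of Table 14.1.10 could not separate a high dose for size from a heavy child.

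The single plot of cohort means adds a second difficulty. It puts a cohort whose doses are derived from weight beside two cohorts whose doses are not, with no common scale that allows for size. Cohorts are formed by background therapy rather than by randomisation, with about 10 to 15 subjects each (SAP 6), so nothing balances age or weight between them.

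Third, averaging over the day's administrations makes the summary depend on dosing frequency. A child moved from TID to QID at an unchanged daily dose would appear to have had a reduction.

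**Working it through.** **Inputs.** Conversion factor 0.0072, and the worked examples for a 35 kg child starting from 65 ng/kg/min (Protocol 6.1.1). Reverse factor 139 (Protocol 6.1.4). Cohort 1 entry range 25-75 ng/kg/min, which may be widened to 25-125 (Protocol 4.1). The documents give no weight distribution. I assume 22 to 70 kg: for Cohort 3 only, "The subject must weigh a minimum of 22 kg at Screening", and 70 kg is where the highest workload band for cycle ergometry begins (Protocol 3.3.1.1).

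**Step 1: reproduce the protocol's figures.** From the table titled "Example TID Dosing Schedule for a 35 kg Subject" and its QID counterpart:
- 0.0072 x 65 x 35 = 16.38 mg/day.
- TID: 16.38 / 3 = 5.46 mg; the table's target is 5.5 mg.
- QID: 16.38 / 4 = 4.095 mg; the table's target is 4.125 mg.
- Both targets total 16.5 mg/day (3 x 5.5 and 4 x 4.125), 0.7% above the equation and consistent with rounding to tablet strengths.
- 1 / 0.0072 = 138.9, which agrees with the 139 in Protocol 6.1.4.

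**Step 2: one intensity, different weights.** At 65 ng/kg/min:

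| Weight (kg) | mg/day | mg per TID dose | mg/kg/day |
|---|---|---|---|
| 22 | 10.3 | 3.43 | 0.468 |
| 35 | 16.4 | 5.46 | 0.468 |
| 70 | 32.8 | 10.92 | 0.468 |

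The spread is 70 / 22 = 3.2-fold, whether per day or per TID dose. Over a narrower assumed range of 25 to 60 kg it is 60 / 25 = 2.4-fold (11.7 to 28.1 mg/day).

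**Step 3: one daily dose, different weights.** 16.5 mg/day is 0.75, 0.47 and 0.24 mg/kg/day at 22, 35 and 70 kg. By the 139 formula these are about 104, 66 and 33 ng/kg/min.

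**Step 4: how much of the Cohort 1 spread could be weight.** By the equation, ln(dose) = ln(0.0072) + ln(Remodulin dose) + ln(weight). If weight and Remodulin dose are independent, weight's share of the log-dose variance is Var(ln weight) / [Var(ln weight) + Var(ln Remodulin dose)]. Simulating 1,000,000 draws from uniform distributions (an assumption):

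| Assumed weights (kg) | 25-75 ng/kg/min | 25-125 ng/kg/min |
|---|---|---|
| 22-70 | 52% | 35% |
| 25-60 | 39% | 24% |
| 22-50 | 36% | 22% |
| 30-50 | 19% | 10% |

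**Step 5: effect of the per-administration definition.** The two regimens in Step 1 have the same daily dose, but SAP 11.1 would record 5.5 mg for one and 4.125 mg for the other, which is 25% lower (1 - 4.125 / 5.5).

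**The case against.** The strongest reply is that mg is the natural unit here. Tablets come in fixed mg strengths, and two of the three cohorts are dosed in fixed mg steps as clinically indicated or as tolerated. The Cohort 1 equation is an optional aid to estimation, and later titration may move a child away from it. Where dose does not follow weight, dividing by weight can add noise. At the initial-dose milestone in Cohorts 2 and 3 it would mainly describe inverse weight and dosing frequency. All of this stands. It is why mg should be kept and why the initial dose is left out of the fix.

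It can also be said that the study is descriptive, that no formal between-cohort test is planned, that dose reached is not a listed objective, and that weights and doses are both listed by subject, so a reader could derive mg/kg. This limits the importance of the point. Separate listings still do not replace a planned summary, and the planned one depends on dosing frequency.

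A reader might go further and infer that mg means reflect weight as much as the dose reached. The documents do not support that: under the assumed ranges weight's share runs from 10% to 52% and passes half in only one of eight scenarios. A reader might also apply the equation to two cohorts of different mean weight and attribute a percentage gap between their mg means to weight alone. That is unsupported too, because only Cohort 1 has a Remodulin dose to convert, and nothing makes Cohort 2 or 3 doses scale with weight.

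**Conclusion.** The point holds as a reporting gap. In Cohort 1, mg means mix weight with dose intensity. The equation implies a 3.2-fold range in mg at one intensity over an assumed 22 to 70 kg, and 2.4-fold over 25 to 60 kg. These figures describe the dose that the equation estimates; doses actually reached may depart from it through titration. For Cohorts 2 and 3 the claim is narrower: mg is the unit in which their dose is set, but the shared plot offers no size-adjusted scale against which to read the three curves. Per-kg scaling would not by itself make the cohorts comparable, since their starting regimens differ. The TID/QID artefact applies to all cohorts and needs no assumption about weight. No primary or secondary endpoint is affected, and nothing here judges any dose right or wrong. It is a low-cost improvement to the exposure reporting.

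**What to change.** In SAP 11.1, keep the mg summaries and add:
- total daily dose in mg/day and in mg/kg/day (daily dose divided by the most recent visit weight) to Table 14.1.10, at the milestones for being off Remodulin, being first off Tyvaso/Ventavis, hospital discharge and final dose;
- a mg/kg/day version of Figure 14.2.5.4.

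Optionally, for Cohort 1, describe the ratio of the daily dose when first off Remodulin to 0.0072 x Baseline Remodulin dose x weight, with median and range. This is an extra rather than a correction, since no objective calls for testing the equation. It has some descriptive interest because Protocol 1.2.3 says it is unknown whether metabolism of the drug is altered in children.

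The cost is SAP wording, two derived variables, some table rows and one figure. Weight is taken at every visit (Protocol 3.3.2.2, SAP 11.6) and dose changes are captured in the eCRF (Protocol 6.1.1 to 6.1.3), so no new data should be needed. One thing to confirm when programming: the dosing listing in SAP 11.1 names only morning, midday and evening doses, so check that the fourth daily dose of QID subjects enters the daily total.
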